To make an accurate diagnosis and treatment planning, we have to obtain images with more details, good resolution and quality which could be achieved by CBCT. However, there are some issues in scanned areas that can affect their quality such as presence of metals (metallic restorations, orthodontic appliances, dental implants, crowns) which result in artifacts which can be considered as an important cause of poor image quality which will lead to poor diagnosis (**Bechara et al., 2012**).

There are many types of artifacts which can be observed on CBCT images. Beam hardening artifact is considered a common one which occurs when an x-ray beam comprised of polychromatic energies passes through an object, resulting in selective attenuation of lower energy photons. The effect is conceptually similar to a high-pass filter, in that only higher energy photons are left to contribute to the beam and thus the mean beam energy is increased ("hardened") (**Shokri et al., 2019**).

Research question:

Can change of milliamperage (mA) and field of view (FOV) reduce the metallic artifacts in CBCT that result from metallic structures?

The aim of this study is to evaluate the effect of exposure parameters as milliamperage (mA) and field of view (FOV) in CBCT on metal artifact of dental implant.

Review of literature:

Databases used: PubMed – Google scholar – Cochrane.

Keywords: CBCT - Metal artifacts - Beam hardening artifact - Dental Implants - MAR–Metal artifacts reduction- metal artifact reduction protocols – mAs - FOV

The first development of Cone beam Computed tomography (CBCT) was originally in 1982 for medical use specially for angiography (**Patcas et al., 2012**).

Then in 1998 the CBCT was introduced for craniofacial scanning, moreover it generates 3D image with a lower cost and lower radiation doses than that in Computed Tomography. The technique of CBCT is depending on a cone-shaped beam of x-ray which is centered on a 2D detector and rotates around the object, providing hundreds of 2D scans of a defined volume of anatomy instead of the slice by slice scanning which was carried out in conventional Computed Tomography (**Alshehri et al., 2012**).

CBCT offers more options for image quality improvement by more than one software and most of these are user- friendly and easy to use with 3D imaging tools. Third party software are available at a wide range of cost, which offer a lot of tools for easy and good diagnosis, analyzing and making appropriate treatment plan. Moreover, third party software are also of help in virtual studying, preparing surgical guides ,etc.... **(Venkatesh & Elluru, 2017).**

The use of CBCT became more common in implant treatment planning as it provides help in minimizing implant complications due to its injury of anatomical structures by offering more accurate details about them **(Alawaji et al., 2018).**

Implant placement has now become part of everyday dental practice and CBCT makes it easier and quicker by providing more accurate detailed images for preoperative treatment planning and evaluation of alveolar ridge morphology (height and width), quality (according to the density of the remaining structure of the bone) and quantity of the available bone for proper implant placement in the most appropriate position to achieve optimum phonetic, esthetic, and masticatory function. Also, CBCT can provide accurate diagnosis of lesions and anatomical structures (inferior alveolar canal, mental foramen, nasal fossa and maxillary sinus) that may limit the placement of osseous implant **(Albelbeisi et al., 2016).**

Despite all advantages of CBCT over multi-slice CT, there are some disadvantages that can interfere with the diagnosis and accurate vision of the images produced. Artifacts can be considered as one of the most important disadvantages of CBCT and when we talk about CBCT and implant we must consider metal artifacts that result from titanium implants in radiation path which can deteriorate the diagnostic image quality significantly **(Parsa et al., 2014).**

Image artifact defined as a visualized structure in reconstructed data which is not visible in the object under investigation. Which interfere with the final diagnostic process, so must know about these artifacts and how to reduce them. These artifacts include extinction artifacts, beam hardening artifacts (metal artifact and cupping artifacts), partial volume effect, aliasing artifacts, ring artifacts and motion artifacts (misalignment artifacts) **(Jaju et al., 2013).**

Beam hardening is considered as one of the most encountered sources of artifacts that are produced when lower-energy photons in the polychromatic x-ray beam are absorbed by a higher attenuating or radiopaque material in preference to high energy photons. The attenuated x-ray beam exits this material with a higher mean energy than the incident or primary beam as it becomes harder or more intense when it reaches the detector. This results in distortion of the attenuated x-ray beam because of differential absorption by the material and produces streaks and dark bands on the image **(Jaju et al., 2013).**

So, beam hardening considered as two different artifacts on the reconstructed images, the appearance of streaks or dark bands and a cupping artifact. Cupping artifacts resulted from passing of x-rays through the large object center which become harder that through the edges due to the greater amount of material that

the beam has to penetrate. So, the final profile of linear attenuation coefficients appears as a cup. But the dark streaks and bands between dense objects which can be seen between two implants in close relation to each other as the beam becomes harder when it passes through both objects than when it passes through only one object (**Jaju et al., 2013**).

Metallic objects in the dental field as implants can produce dark artifacts, induced by scattering, and streak artifacts, making anatomical structures mysterious and affecting the contrast between adjacent areas at region of interest. As this metallic material highly attenuates the x-ray beam, the attenuation values of objects behind the object are incorrectly high. Due to the cone shaped beam of CBCT, the metallic streak artifacts occur in all directions from the high attenuation object (**Parsa et al., 2014**).

Many types of software and imaging protocols have been developed trying to solve the problem of the effect of the artifacts on the final CBCT image. So, manufacturers tried to minimize beam hardening by using filtration, anti-scatter grids, calibration correction, and beam hardening correction software. (**Jaju et al., 2013**).

A lot of parameters such as X-ray beam quantity and quality, rotation arc, field of view (FOV) and pixel size can affect the CBCT image quality and image characteristics that may include artifacts, contrast resolution and noise. Metal artifact is considered as one of the most factors that degrading the image quality (**Panjnough et al., 2016**).

Field of view is one of the most important hardware tools that must be determined carefully to get more reliable and accurate measurements (**Abdelkarim, 2019**).

FOV must be determined according to the needs of the case.

Small FOV devices range normally from 5 to 10 cm, which give a 3D view of a single tooth unit and its surrounding anatomy. They are used for individual tooth assessment (e.g; impacted teeth, root morphology, supernumeraries, sites for placement of dental implants, and temporary anchorage devices). Medium FOV provides single jaw anatomy, whereas the maxillomandibular FOV gives the clinician an understanding of two-jaw anatomy, temporomandibular joint (TMJ), and occlusion. They are used for more information on facial asymmetries, bilateral TMJ evaluations and occlusal relationships.

In addition, Large or craniofacial FOVs include the cranial base, cranium and all associated structures. The large FOVs involve most of the whole head which help clinicians to assess relationships between skeletal bases, between teeth and skeletal bases, and also can be significant for anomalies in patients requiring orthognathic surgery or those with craniofacial anomalies (**Kau and Ortho, 2014**).

In a study done by **Shokri et al**, to evaluate the effect of exposure parameters of milliampere (mA) and field of view (FOV) of CBCT image on a metal artifact of dental implants by using of 27 bone blocks with different densities (nine were type 1, nine were types 2 and 3, and nine were type 4). These blocks were placed in mandibular wax models. Then scanned after drilling and implant placement using Cranex3D imaging system with a $4 \times 6 \text{ cm}^2$ and $6 \times 8 \text{ cm}^2$ FOV and 4 and 10 mA. Gray value of the bone blocks was

recorded before and after placement of implants. And the result was that the amount of artifacts was lower in small FOV compared to large FOV ($P < 0.05$). Change of mA had no effect on metal artifacts ($P > 0.05$). Artifacts in type 4 bone were greater than in other bone types ($P < 0.05$). Difference between type 1 and types 2 and 3 was not significant ($P > 0.05$).

Study objectives and hypotheses:

Study objectives:

The objective of this study will be the evaluation of the effect of variation of the exposure parameters FOV & mA on the produced metallic artifact induced by dental implants that affect the CBCT image using linear measurements of dental implant dimensions.

Study hypotheses:

Is the variation of Field of view (FOV) and milliamperere (mA) can affect the CBCT image quality with metal artifacts?

III. Methods

A) Samples, intervention and outcomes

7. Calculated sample size

A power analysis was designed to have adequate power to apply a statistical test of the null hypothesis that there is no difference between tested groups. By adopting an alpha level of (0.05) a beta of (0.2) i.e., power=80% and an effect size (f) of (0.38) calculated based on the results of a previous study¹; the predicted sample size (n) was a total of (80) cases. Sample size calculation was performed using G*Power version 3.1.9.7²

8. Description of study sample

- 4 dry human mandibles will be obtained from faculty of medicine from Cairo University.
 - Layers of dental wax for soft tissue stimulation from dental store of El-Kasr El-Einy, faculty of dentistry, Cairo University.
 - 8 dental implants will be obtained from Roots Company.
 - Each dry human mandible with implant will be scanned in the Oral and Maxillofacial Radiology Department, Faculty Dentistry, Cairo University using CBCT machine Planmeca ProMax® 3D Mid.
 - Produced CBCT images will be analyzed by using Romexis ® software (planmeca Helsinki-Finland) for measuring dental implant dimensions (length and width) using linear measurements on software and real measurements of dental implants as a reference standard.
-

9. Intervention for each group

- Each mandible will be prepared and drilled for implant placement at the middle of the bone at the area of interest
- Two layers of wax will be applied over them for soft tissue stimulation.
- Then each mandible will be scanned by using CBCT machine Planmeca ProMax® 3D Mid in the Oral and Maxillofacial Radiology Department, Faculty Dentistry, Cairo University 4 times with 4 different protocols of FOV (40 × 50 mm & 100 × 60 mm) and mA (8 and 10) by the following:
 - First:
 - mA 8 and FOV 40 × 50
 - mA 8 and FOV 100 × 60
 - mA 10 and FOV 40 × 50
 - mA 10 and FOV 100 × 60
 - Second:
 - mA 8 and FOV 40 × 50
 - mA 8 and FOV 100 × 60
 - mA 10 and FOV 40 × 50
 - mA 10 and FOV 100 × 60
 - Third:
 - mA 8 and FOV 40 × 50
 - mA 8 and FOV 100 × 60
 - mA 10 and FOV 40 × 50
 - mA 10 and FOV 100 × 60
 - Fourth:
 - mA 8 and FOV 40 × 50
 - mA 8 and FOV 100 × 60
 - mA 10 and FOV 40 × 50
 - mA 10 and FOV 100 × 60
- Each CBCT image Produced will be analyzed for metal artifact by using Romexis ® software (planmeca Helsinki-Finland) for measuring dental implant dimensions (length and width) using linear measurements

10. Outcomes

The primary outcome of this study will be the assessment of Implants dimensions measurements that will be measured by using linear measurement on Romexis® software (Planmeca-Helsinki-Finland) for each scan to evaluate the effect of FOV and mA on artifacts induced by dental implants.

Prioritization of Outcome	Method of Measurement	Unit of Measurement
Assessment of implants dimensions measurements accuracy	Linear measurements	Millimetres (mm)

B) Assignment to intervention

The randomization will be applicable.

11. Sequence generation

Mechanism used to implement the random allocation sequence is that mandibles will be sequentially numbered.

12. Allocation concealment

Opaque sealed envelopes will be used to conceal the sequence until intervention is assigned.

12. Implementation:

The main supervisor will be responsible for the random allocation sequence and enrolling mandibles, but the co-supervisor and the researcher will be responsible for assignment for intervention.

C) Blinding

14. Blinding

The Co-supervisor and investigator will be blinded.

D) Statistical methods

Handling of numerical/ quantitative variables:

Numerical data will be explored for normality by checking the data distribution, calculating the mean and median values and using Kolmogorov-Smirnov and Shapiro-Wilk tests. If the data was found to be normally distributed, it will be presented as mean and standard deviation values. If the assumption of normality was found to be violated, the data will be presented as median and range values.

Handling of categorical/ qualitative variables:

Categorical data will be represented as frequency (n) and percentage (%).

Statistical methods:

Categorical data will be represented as frequency (n) and percentage (%) and will be analyzed using chi square test. Numerical data will be explored for normality by checking the data distribution, calculating the mean and median values and using Kolmogorov-Smirnov and Shapiro-Wilk tests. If the data was found to be normally distributed, it will be presented as mean and standard deviation values and one-way ANOVA followed by Tukey's post hoc test will be used for the analysis.

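### The objective asks about mA in general, but only 8 v 10 mA is tested: a narrow, unexplained contrast that cannot support a general statement about mA

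*Combined protocol and SAP*

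**What the plan says.** The Research question is general: "Can change of milliamperage (mA) and field of view (FOV) reduce the metallic artifacts in CBCT that result from metallic structures". Study objectives repeats it as the "evaluation of the effect of variation of the exposure parameters FOV & mA on the produced metallic artifact", so mA is one of two named factors.

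Section 9 (Intervention for each group) gives the levels. Each mandible is scanned "4 times with 4 different protocols of FOV (40 × 50 mm & 100 × 60 mm) and mA (8 and 10"), a 2 x 2 crossing of FOV and mA.

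The Review of literature describes one study in detail. It used two FOVs and two mA settings ("FOV and 4 and 10 mA"), and its mA result is reported as "Change of mA had no effect on metal artifacts" (P > 0.05), with no estimate, SD or interval. Its outcome was gray value of bone blocks on a different scanner. The outcome here, in section 10, is "Assessment of implants dimensions measurements accuracy", in millimetres.

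Section 7 states: "By adopting an alpha level of (0.05) a beta of (0.2) i.e., power=80% and an effect size (f) of (0.38"), for a difference between tested groups, giving 80 cases. Section 8 lists 4 mandibles and 8 implants. Section D plans one-way ANOVA with Tukey's test or, if normality fails, Kruskal-Wallis with Bonferroni-corrected Mann-Whitney tests. No section explains why 8 and 10 mA were chosen.

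**The concern.** With only two levels of a factor, the distance between them decides how much a result can say about it. The question is open-ended, the step is small, and the protocol's own precedent used a step three times as wide in mA with the same upper level. The protocol neither justifies the narrower step nor says what size of mA effect it expects or could detect.

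At stake is the interpretation of half the objective. If the mA comparison is not significant, three explanations remain: mA has no effect on implant measurements, the step was too small to show one, or the test was too weak. The plan as written could not separate them.

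**Working it through.** **1. The plan's own figure.** Inputs from section 7: f = 0.38, alpha 0.05, power 80%. For a one-way ANOVA with k = 4 groups, the noncentrality is f² x N = 0.1444 x 80 = 11.55 on 3 and 76 df. Power is 0.803, and 80 is the smallest N that reaches 0.80. The stated N therefore reproduces as an omnibus test among the four protocols. It is not a calculation for mA.

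**2. Width of the mA step.** Levels come from section 9 and the Review of literature.
- This study: 10 − 8 = 2 mA; 10/8 = 1.25.
- Precedent: 10 − 4 = 6 mA; 10/4 = 2.5.
- Share of the earlier span: 2/6 = 33% on a linear scale, or ln(1.25)/ln(2.5) = 0.2231/0.9163 = 24% on a log scale.

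**3. What the planned test can detect for mA.** One-way ANOVA with Tukey gives six pairwise comparisons. Two isolate mA: 8 v 10 at the small FOV and 8 v 10 at the large FOV. Observations are treated as independent, as the plan does. The noncentrality is d√(n/2), and the critical value is the studentized range quantile divided by √2.
- n = 20 per group (80/4): critical value 2.63 on 76 df; 80% power needs d = 1.10.
- n = 8 per group (8 implants under each protocol, 32 in all): critical value 2.73 on 28 df; 80% power needs d = 1.80.

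Both cases are shown because section 7 does not say what one of the 80 cases is.

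**4. The same data with mA as a main effect.** Pooling over FOV gives one df and noncentrality (d/2)² x N. The detectable d is 0.63 at N = 80 and 1.03 at N = 32. This is better than step 3, but the plan does not specify it.

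**5. Illustration only.** The documents give no mA effect, so assume a 4 v 10 effect of d = 0.5, 0.76 (twice the stated f) or 1.0, scaled to the narrower step. Power for the mA main effect, with independent observations:

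| Assumed d, 4 v 10 | Linear: d for 8 v 10 | Power, N = 80 | Power, N = 32 | Log scaling: power, N = 80 |
|---|---|---|---|---|
| 0.5 | 0.17 | 11% | 7% | 8% |
| 0.76 | 0.25 | 20% | 11% | 13% |
| 1.0 | 0.33 | 31% | 15% | 19% |

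**6. What pairing could recover.** Take each implant's 8 v 10 difference, averaged over the two FOVs, with 8 implants. The SD of that average is √(2(1−ρ))/√2 = √(1−ρ), treating the differences at the two FOVs as independent. The noncentrality is d√8/√(1−ρ) on 7 df. For d = 0.25, power is 14%, 28%, 50% and 78% at ρ = 0.5, 0.8, 0.9 and 0.95. The documents give no correlation, so all four are assumptions.

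**The case against.** The best defence is that section 9 names the levels openly and that an 8 v 10 difference is a legitimate quantity that can be estimated. Two nearby settings may be the practical choice, although the protocol does not say so. This stands in part. A reader might infer that the mA half of the objective cannot be answered at all; the documents do not support that. As step 6 shows, a paired analysis could detect a fairly small effect if within-implant correlation were high, and nothing in the documents rules that out.

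A reader might also infer that a null result is close to predetermined because 8 to 10 mA lies within a range already reported as null. That does not follow. A P value above 0.05 without an estimate or interval does not show absence of effect, and the earlier study used another scanner and a gray-value outcome. Nothing in the documents links that outcome to error in millimetres. For the same reason, a multiple of the sample size scaled from the earlier mA effect, or an argument from image noise, has no anchor in the documents.

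The defence can add that widening the step merely returns to a contrast already reported as null. But the case for widening does not depend on that null: for the question as worded, a wider contrast makes either result more informative. Finally, mA and FOV have no common scale, so unequal relative spacing is not in itself an error. The machine's mA range and other exposure settings are not given, so feasibility must be checked.

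**Conclusion.** The point holds as a mismatch between a general question and a narrow contrast. The mA step is 1.25-fold and one third of the precedent's span, it is unexplained, and the sample size was not set for it. The planned pairwise tests would need an mA difference of about 1.1 SD (20 per group) or 1.8 SD (8 per group) for 80% power. Those two figures assume independent observations. The 8% to 31% power range at N = 80 also assumes the size and scaling of an effect that the documents never quantify, so it is illustrative.

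The study can still estimate 8 v 10 mA. What it could not do, if that comparison were non-significant, is support a statement about mA in general. This is an inexpensive improvement best made before scanning, not a fatal flaw.

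**What to change.** Keep the 2 x 2 design and the number of scans, and set the two mA levels further apart, as far as the machine allows with other settings fixed. The investigator chooses the levels and states the reason in section 9. The specimens are dry mandibles, so this adds no scans, implants or patient exposure. The small downside is that one level may be less typical of routine use.

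If 8 and 10 mA are kept:
- Restate the research question and objective as the effect of 8 v 10 mA.
- In section D, estimate the mA main effect within implant, across both FOVs, with a 95% CI, instead of relying on pairwise one-way ANOVA comparisons.
- Limit the conclusion to those two levels.

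This fallback costs a few sentences and one changed analysis, with no new data. Under either option, section 7 should state the mA difference in millimetres that the study can detect and the SD and within-implant correlation assumed for it.

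### The stated randomisation orders nothing: mandibles that all receive all four protocols are merely numbered, and if the list in section 9 is the run order, mA, FOV and their interaction are aliased with scan position

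*Combined protocol and SAP*

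**What the plan says.** Section 8 sets the specimens: "4 dry human mandibles will be obtained from faculty of medicine from Cairo University", with eight implants. Section 9 has each mandible scanned "4 times with 4 different protocols of FOV (40 × 50 mm & 100 × 60 mm) and mA (8 and 10"). It then prints four blocks, headed First to Fourth. Each block holds the same four lines in the same order: 8 mA small FOV, 8 mA large FOV, 10 mA small FOV, 10 mA large FOV. The blocks are not labelled as mandibles, and nothing says that the lines are in the order of scanning.

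On allocation, part B states: "The randomization will be applicable". Section 11 gives the mechanism: "Mechanism used to implement the random allocation sequence is that mandibles will be sequentially numbered". The allocation concealment section has sealed envelopes hiding a sequence until assignment, but does not say what that sequence is a sequence of. No random or counterbalanced scan order appears anywhere.

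The statistical methods section plans one-way ANOVA with Tukey comparisons, or Kruskal-Wallis with Mann-Whitney tests. Neither has a term for mandible or scan position.

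**The concern.** When every specimen receives every treatment, there is no allocation between specimens to randomise or conceal. What can be randomised is the order in which each specimen is scanned and, later, the order in which the images are measured. The plan applies its randomisation wording to the one step where it can have no effect and leaves scan order undefined.

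The effects of mA and FOV are the whole objective of the study, and the outcome is a linear measurement in millimetres. If all specimens are scanned in one fixed order, anything that changes steadily over a session is read as an effect of the settings. Possible sources are scanner output, wax that shifts with handling, and the operator's set-up. If the images are also measured in scan order, reader learning is another.

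**Working it through.** **The plan's own figure.** Section 7 gives alpha 0.05, power 80%, f = 0.38 and "the predicted sample size (n) was a total of (80) cases". For a one-way ANOVA the noncentrality is λ = f² × N = 0.1444 × 80 = 11.55. With four groups (taken from the four protocols; section 7 does not state the number) and 3 and 76 degrees of freedom, power is 0.803. At N = 76 it is 0.779. The 80 therefore reproduces. Scan order does not enter this formula, so neither the problem nor the fix changes it.

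**What the numbering allocates.** Four mandibles × four protocols = 16 scans, taking one block per mandible. Every mandible-protocol pair occurs once, however the mandibles are numbered. Renumbering changes nothing that is compared.

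**Positions if the list is the run order.**

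| Position | mA | FOV |
|---|---|---|
| 1 | 8 | small |
| 2 | 8 | large |
| 3 | 10 | small |
| 4 | 10 | large |

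- mA: mean position (1 + 2)/2 = 1.5 at 8 mA and (3 + 4)/2 = 3.5 at 10 mA, a difference of 2.
- FOV: mean position (1 + 3)/2 = 2 for small and (2 + 4)/2 = 3 for large, a difference of 1.
- Interaction: (1 + 4)/2 − (2 + 3)/2 = 0.

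A linear drift of d mm per scan therefore adds 2d to the mA contrast, 1d to the FOV contrast and nothing to the interaction. The documents give no d. Purely as assumed values:

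| d (mm per scan) | Shift in mA contrast | Shift in FOV contrast |
|---|---|---|
| 0.01 | 0.02 | 0.01 |
| 0.05 | 0.10 | 0.05 |
| 0.10 | 0.20 | 0.10 |

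**Whether it can be adjusted out.** With mA and FOV coded −1/+1, position = 2.5 + 1.0 × mA + 0.5 × FOV. This gives exactly 1, 2, 3 and 4 for the four lines. Linear position is thus an exact combination of the two factors, and a model holding all three cannot be fitted. With position as a four-level factor alongside mandible, mA, FOV and the interaction each add rank 0 to the design matrix, so all three are fully aliased.

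**A counterbalanced order.** Let A = 8 mA small, B = 8 mA large, C = 10 mA small, D = 10 mA large, and take the rows ABDC, BCAD, CDBA, DACB. The columns read ABCD, BCDA, DABC and CDAB, so each protocol occurs once in each position. The neighbouring pairs are AB, BD, DC; BC, CA, AD; CD, DB, BA; DA, AC, CB: all 12 ordered pairs, once each. Mean position is 2.5 at every level of mA and FOV, so both drift biases become 0. mA, FOV and the interaction are then all estimable after adjustment for mandible and position.

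**The case against.** The strongest reply is that the list is not a run order. It is the usual way to write out a 2 × 2 set of conditions, the ordinals number the blocks and not the scans, and the envelopes imply that some sequence exists. This stands. A reader might infer from section 9 that mA is fully confounded with period, as a fact of the design. The documents do not support that, because they never state the run order. Nor would the problem be particular to mA: under the listed order FOV and the interaction are aliased with categorical position just as completely, and mA is worse off than FOV only under a linear drift.

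The blocks might also be four repeat rounds on each mandible. One block per mandible is the natural reading with four mandibles, but it is not stated. With repeat rounds, each protocol recurs four scans later, so a smooth drift could be estimated from the change between rounds. The statement that it cannot be adjusted out would then fail for that kind of drift. The unadjusted shifts of 2d and 1d would remain, and the planned analysis makes no such adjustment.

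Finally, the outcome is the measured size of metal implants in dry bone. Biological carryover does not arise, loosening does not change an implant's dimensions, and repositioning is more likely to add scatter than a steady trend. This also stands: d may be small, and nothing in the documents shows that it is not. None of it supplies the missing randomisation.

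**Conclusion.** The point holds without conditions in one respect: as specified, nothing is randomised, because the only mechanism is the sequential numbering of mandibles that all receive all four protocols. The concealment has nothing defined to conceal.

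The consequence is conditional. It assumes that the printed list is the run order and that each block is one mandible. Then mA, FOV and their interaction cannot be separated from scan position, and a linear drift biases mA by 2d and FOV by 1d. The size of d is unknown, so no actual bias has been shown. If the list is not the run order, the protocol states no run order at all, and the same correction is needed. It should be made before scanning, since a fixed order cannot be repaired in the analysis.

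**What to change.** - **Sections 9, 11 and 12:** state that the envelopes hold the scan order within each mandible, and that this order is randomised or counterbalanced. One suitable scheme allocates the four mandibles at random to the rows ABDC, BCAD, CDBA and DACB, with the labels defined in the working. Any other randomised or counterbalanced order would also serve, since balance for carryover is not essential here.
- **Section 9:** replace the four identical lists with these sequences, and say whether First to Fourth are mandibles or repeat rounds. If they are rounds, give each round its own order.
- **Data collection:** record the scan position of every scan, so that a trend can be examined.
- **Measurement:** measure the images in a separately randomised order that does not follow scan order. Balancing the scans does not protect against learning during measurement.

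The cost is protocol wording and a short allocation list. The number of scans is unchanged, as is the section 7 calculation. The only practical burden is changing the FOV and mA settings in a different order for each mandible.

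### The stated randomisation allocates nothing, the blinded co-supervisor also has an assigning role, and no described procedure protects the reading of the images

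*Combined protocol and SAP*

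**What the plan says.** All references are to the combined protocol and SAP.

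- **Assignment to intervention (B):** "The randomization will be applicable".
- **Sequence generation (11):** "Mechanism used to implement the random allocation sequence is that mandibles will be sequentially numbered".
- **Allocation concealment (12):** "Opaque sealed envelopes will be used to conceal the sequence until intervention is assigned".
- **Implementation:** one person holds the sequence: "The main supervisor will be responsible for the random allocation sequence and enrolling mandibles". Two others assign: "but the co-supervisor and the researcher will be responsible for assignment for intervention".
- **Blinding (14):** "The Co-supervisor and investigator will be blinded". This is the whole of the section.
- **Intervention for each group (9):** every mandible is scanned four times, once under each combination of two fields of view (40 × 50 and 100 × 60 mm) and two mA values (8 and 10). The same four combinations are printed in the same order in each of four blocks. On analysis, "Each CBCT image Produced will be analyzed for metal artifact by using Romexis" software; the reader is not named.
- **Outcomes (10):** the outcome is "Assessment of implants dimensions measurements accuracy", in millimetres, from linear measurements. Section 8 makes the real implant measurements the reference standard.

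**The concern.** The plan uses the vocabulary of a parallel-group trial (sequence, envelopes, assignment), but the experiment is fully crossed. Those safeguards therefore sit at a step where nothing is decided. The step where judgement can enter, measuring an implant on screen, has no described safeguard.

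The one sentence on blinding names a person who also has an assigning role. Someone who assigns the scan settings knows them, unless the images are later coded, and no coding is described.

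At stake is the primary outcome. The same implants are measured under each protocol, next to a true value that may be known. A reader who recalls an earlier value or knows the real length may pull readings together and hide a real difference between protocols. A reader who knows the field of view may push them apart. Once unmasked readings have been made, those conditions cannot be restored.

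**Working it through.** No figure in the plan bears directly on this point, so the check compares sections and counts what the design produces.

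**1. Roles**

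| Role | Holder as stated |
|---|---|
| Holds sequence, enrols mandibles | Main supervisor |
| Assigns intervention | Co-supervisor and researcher |
| Blinded | Co-supervisor and investigator |
| Measures the images | Not stated |

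The co-supervisor appears in two rows with nothing to connect them. If the researcher and the investigator are one person, both blinded people are also assigners. The documents do not say whether they are.

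**2. Is there anything to allocate?**

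- Protocols: 2 FOV × 2 mA = 4.
- Mandibles (section 8): 4.
- Scans per mandible (section 9): 4, one per protocol.
- Scans as written: 4 × 4 = 16.

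Every protocol is applied to 4 of 4 mandibles, so no mandible receives one protocol rather than another. There is no between-mandible allocation to randomise or conceal. Sequential numbering only labels the specimens and has no random element in any case.

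**3. What could still be randomised?** Only the order of scanning and the order of reading. The plan randomises neither.

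**4. Which stage does each safeguard cover?**

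- Numbering: labels specimens before scanning.
- Envelopes: act only until assignment, which precedes any reading.
- Blinding: no stage, object or method is given.
- Reading: the plan does not give the reading order. It does not say whether the reader sees the scan settings, the real dimensions or earlier readings of the same implant.

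**5. How often is the same implant seen?** This is conditional on each of the 8 implants being imaged once under each protocol and read once per image:

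- Implant-images: 8 × 4 = 32.
- Readings: 32 × 2 dimensions (length, width) = 64.
- Readings per implant dimension: 64 / (8 × 2) = 4.

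Under that assumption, each true length or width is measured four times.

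**6. Size and direction.** The documents give no reader-error or measurement-variance figure, so the bias cannot be expressed in mm. A direction for expectation is cited for FOV only. The study described in the Review of literature reported fewer artifacts at small FOV and no effect of mA, but it recorded grey values. Carry-over to linear measurements is an inference. Recall and knowledge of true size act the other way, toward no difference.

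**The case against.** **The roles can coexist.** A person may assign scans and later read coded images blind, so the two sentences are not strictly incompatible. This stands. A reader might infer that blinding of the co-supervisor is impossible, and the documents do not support that. They show two roles left unreconciled, with no coding step that would make both workable. The overlap also affects the outcome only if that person reads the images, which is not stated.

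**The intent to blind is there.** The sentence in section 14 may well be meant for the readers, so the gap could be called missing detail. This stands only in part. The procedures that are described, followed as written, would still leave the measurement unprotected.

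**Manual reading is inferred.** The plan says linear measurement on software and names neither an operator nor an automated method. This stands, and the point is weaker if the measurement is automated.

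**The counts depend on layout.** If one small-field scan captured only one implant, there would be 8 × 2 + 4 × 2 = 24 scans. If the four printed blocks were repeat rounds and not the four mandibles, there would be 4 × 16 = 64. The text of section 9, four scans per mandible, gives 16. The conclusion is the same under any of these counts.

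**The remedy may fail where it matters most.** FOV may be recognisable even after cropping, and FOV is the factor with a cited expectation. This stands as a limit on the benefit. Acquisition labels, reading order and earlier readings can still be masked.

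**Conclusion.** The concern holds on the text. The randomisation as described has no random element and nothing to act on, the co-supervisor's two roles are not reconciled, and no stated procedure protects the primary measurement. It affects all 16 scans as written; the 32 implant-images and 64 readings apply only under the condition given in the working.

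A reader might go further and infer that the results will favour the small field of view, or that the person measuring is known to be unblinded. The documents support neither. The reader is unnamed, the possible biases run in opposite directions, and their size cannot be derived. The conclusion assumes that a person places the measurements and that the four printed blocks describe the four mandibles. It warrants a change before any image is read.

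**What to change.** Revise the sections on assignment, sequence generation, concealment, implementation and blinding as follows.

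- State that every mandible receives all four protocols and that there is no between-mandible allocation.
- Replace sequential numbering with a computer-generated random reading order of coded images. The main supervisor, who already holds the sequence, keeps the code list.
- Name as reader someone who does not set up or order the scans. If the co-supervisor or the investigator is to be the blinded reader, remove that person from assignment.
- During reading, hide acquisition labels, real implant dimensions and earlier readings, and show the same cropped region for every image.

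**Cost:** protocol wording, a code list and a little extra work for the main supervisor, with no additional scans or specimens. Masking of FOV may be incomplete despite cropping. Masking of true size may be incomplete if the implants share one nominal size or if the reader placed them, neither of which is stated. The bias is reduced, not removed.
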